16.2 Appendix 2: Liver event and laboratory trigger definitions & follow-up requirements

Table 16-1 Definitions of Triggers, Actions and Follow-up requirements for liver events

Criteria	Actions required	Follow-up monitoring
Potential Hy's Law case (Elevated ALT/AST > 3 × ULN and TBL > 2 × ULN but without notable increase in ALP to > 2 × ULN – or 3 x ULN in the presence of bone pathology)	
 Discontinue the study treatment immediately (if possibly related to study treatment) Hospitalize, if clinically appropriate Establish causality (investigate alternative etiologies)^a Record the AE and contributing factors (e.g. concomitant medication, medical history, laboratory value) in the appropriate eCRF 	
 ALT, AST, TBL, Alb, PT/INR, ALP, GGT, CK and GLDH (frequency at Investigator discretion) Monitor for symptoms^b Report outcome^c
ALT		
> 8 × ULN	
 Interrupt the study treatment (if possibly related to study treatment) Hospitalize if clinically appropriate Establish causality (investigate alternative etiologies)^a Record the AE and contributing factors (e.g. con meds, med hx, lab) in the appropriate eCRF 	
 ALT, AST, TBL, Alb, PT/INR, ALP and GGT (frequency at Investigator discretion) Monitor for symptoms^b Report outcome^c
> 3 × ULN and INR > 1.5 (in the absence of anticoagulation) If elevated at baseline: > 2 x baseline or > 300 U/L (whichever occurs first)	
 Interrupt the study treatment (if possibly related to study treatment) Hospitalize if clinically appropriate Establish causality (investigate alternative etiologies)^a Study drug can be restarted only if alternative etiology is identified and liver enzymes return to baseline Record the AE and contributing factors (e.g. con meds, med hx, lab) in the appropriate eCRF 	
 ALT, AST, TBL, Alb, PT/INR, ALP and GGT until resolution (frequency at Investigator discretion)
> 5 to ≤ 8 × ULN If elevated at baseline: > 3 x baseline or > 300 U/L (whichever occurs first)	
 Repeat LFT within 48 hours If elevation persists, continue follow-up monitoring If elevation persists for more than 2 weeks, discontinue the study drug Establish causality (investigate alternative etiologies)^a 	
 ALT, AST, TBL, Alb, PT/INR, ALP and GGT until resolution (frequency at Investigator discretion)

Criteria	Actions required	Follow-up monitoring
	
 Record the AE and contributing factors (e.g. con meds, med hx, lab) in the appropriate eCRF 	

> 3 × ULN to ≤ 5 × ULN (accompanied by symptoms)^b
 
If elevated at baseline: > 2 x baseline or > 300 U/L (whichever occurs first)
	
 Interrupt the study treatment (if possibly related to study treatment) Hospitalize if clinically appropriate Establish causality (investigate alternative etiologies)^a Study drug can be restarted only if alternative etiology is identified and liver enzymes return to baseline Record the AE and contributing factors (e.g. con meds, med hx, lab) in the appropriate eCRF 	
 ALT, AST, TBL, Alb, PT/INR, ALP and GGT until resolution (frequency at Investigator discretion) Monitor for symptoms^b Report outcome^c

> 3 to ≤ 5 × ULN (patient is asymptomatic)^b
 
If elevated at baseline: > 2 x baseline or > 300 U/L (whichever occurs first)
	
 Repeat LFT within the next week If elevation is confirmed, initiate close observation of the participant 	
Investigator discretion Monitor LFT within 1 to 4 weeks

ALP (isolated)		

> 2 × ULN (in the absence of known bone pathology)
 
>3 x ULN in the presence of if bone pathology
	
 Repeat LFT within 48 hours If elevation persists, establish causality (investigate alternative etiologies)^a Record the AE and contributing factors (e.g. con meds, med hx, lab) in the appropriate eCRF 	
Investigator discretion Monitor LFT within 1 to 4 weeks or at next visit

Liver events		
Jaundice	
 Interrupt the study treatment (if possibly related to study treatment) Hospitalize the participant Establish causality (investigate alternative etiologies)^a Study drug can be restarted only if alternative etiology is identified and liver enzymes return to baseline 	
 ALT, AST, TBL, Alb, PT/INR, ALP and GGT until resolution (frequency at Investigator discretion) Monitor symptoms^b Report outcome^c

Criteria	Actions required	Follow-up monitoring
	
 ● Record the AE and contributing factors (e.g. con meds, med hx, lab) in the appropriate eCRF 	
Any AE potentially indicative of a liver toxicity ^d	
 ● Consider study treatment interruption or discontinuation ● Hospitalization if clinically appropriate ● Establish causality (investigate alternative etiologies)^a ● Record the AE and contributing factors (e.g. con meds, med hx, lab) in the appropriate eCRF 	Investigator discretion

^a Serology tests, imaging and pathology assessments, hepatologist's consultancy; obtaining more detailed history of symptoms and prior or concurrent diseases, history of concomitant drug use, exclusion of underlying liver disease

^b Severe fatigue, malaise (general), abdominal pain (right upper quadrant), nausea, vomiting or rash with eosinophilia

^c Resolved = return to Day 1 values; Condition unchanged = stable values at three subsequent monitoring visits at least 2 weeks apart; Condition deteriorated = values worsen or liver transplantation; and Fatal.

^d These events cover the following: hepatic failure, fibrosis and cirrhosis, and other liver damage-related conditions; the non-infectious hepatitis; the benign, malignant and unspecified liver neoplasms.

ALP: alkaline phosphatase; GLDH: glutamate dehydrogenase TBL: total bilirubin; ULN: upper limit of normal

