5.2 Exclusion criteria

Participants meeting any of the following criteria are not eligible for inclusion in this study.

1. Participation in any other investigational drug trial or use of other investigational drugs at the time of enrollment, or within 5 elimination half-lives of enrollment, or within 30 days of enrollment, whichever is longer; or longer if required by local regulations.
2. Prior treatment with a complement inhibitor, including anti-C5 antibody.
3. History of hypersensitivity to iptacopan or any of its excipients or to drugs of similar chemical classes.
4. Known or suspected hereditary complement deficiency.
5. History of hematopoietic stem cell transplantation.
6. Patients with laboratory evidence of bone marrow failure (reticulocytes $<100 \times 10^9/L$, platelets $<30 \times 10^9/L$, neutrophils $<0.5 \times 10^9/L$).
7. Active systemic bacterial, viral (incl. COVID-19) or fungal infection within 14 days prior to study drug administration.
8. Presence of fever ≥ 38 °C (100.4 °F) within 7 days prior to study drug administration.
9. Human immunodeficiency virus (HIV) infection (known history of HIV or test positive for HIV antibody at Screening).
10. History of recurrent invasive infections caused by encapsulated organisms, e.g. meningococcus or pneumococcus.

11. Major concurrent comorbidities including but not limited to: severe kidney disease (e.g., eGFR<30 mL/min/1.73m², dialysis), advanced cardiac disease (e.g., NYHA class IV heart failure), severe pulmonary disease (e.g., severe pulmonary hypertension (WHO class IV)), or hepatic disease (e.g., active hepatitis) that in the opinion of the investigator precludes participant's participation in the study.
12. Liver disease, such as active hepatitis B virus (HBV) or hepatitis C virus (HCV) infection defined as HBsAg positive or HCV RNA positive, or liver injury as indicated by abnormal liver function tests at Screening:
 - Any single parameter of alanine aminotransferase (ALT), gamma-glutamyl transferase (GGT), alkaline phosphatase must not exceed 3 × ULN.
13. Unstable medical condition including, but not limited to, myocardial ischemia, active gastrointestinal bleeding, coexisting chronic anemia unrelated to PNH, or unstable thrombotic event not amenable to active treatment as judged by the investigator at Screening.

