For selected laboratory parameters, abnormalities occurring at any time-point from scheduled, unscheduled and premature discontinuation visits considering all post-baseline on-treatment data will be summarized. Where normal ranges are available, abnormalities in laboratory data will be listed by participant and visit/time.

Liver toxicities

A criterion-based table for selected liver function tests and AEs will be presented including the number and percentage of the events described in [Table 2-2](#). In the PNH indication, aspartate aminotransferase (AST) can increase for reasons not related to liver toxicity and therefore should not be considered in the derivation of liver toxicities. Moreover INR is routinely monitored and can be used for the definition of liver function events. Events for the PNH indication are described in [Table 2-2](#).

Liver toxicity finding based on laboratory values and accounting for presence of bone pathology, symptoms, Gilbert syndrome will be presented. AEs collected in the analysis dataset and related

to liver toxicities (Jaundice, AE potentially indicative of a liver toxicity) will either be reported separately in a specific table or will simply be displayed as part of the general AE tables.

Table 2-2 Liver Toxicities

Definition	Label for output display
Potential Hy's Law case	
(ALT or AST > 3 × ULN) and TBL > 2 × ULN and ALP to ≤ 2 × ULN in the absence of bone pathology ^a (ALT or AST > 3 × ULN) and TBL > 2 × ULN and ALP to ≤ 3 × ULN in the presence of bone pathology ^a	Potential Hy's Law case
ALT elevations	
If ALT ≤ ULN at baseline: (ALT > 3 × ULN) and INR > 1.5 If ALT > ULN at baseline then criteria for ALT are defined as ALT > 2 x baseline or > 300 U/L and INR > 1.5	(ALT > 3 × ULN) and INR > 1.5
ALT > 8 × ULN	ALT > 8 × ULN
If ALT ≤ ULN at baseline: ALT > 5 to ≤ 8 × ULN If ALT > ULN at baseline then criteria for ALT are defined as ALT > 3 x baseline or > 300 U/L	ALT > 5 to ≤ 8 × ULN
If ALT ≤ ULN at baseline: ALT > 3 to ≤ 5 × ULN (accompanied by symptoms) ^a If ALT > ULN at baseline then criteria for ALT are defined as ALT > 2 x baseline or > 300 U/L (accompanied by symptoms) ^a	ALT > 3 to ≤ 5 × ULN with symptoms
If ALT ≤ ULN at baseline: ALT > 3 to ≤ 5 × ULN (patient is asymptomatic) ^a If ALT > ULN at baseline then criteria for ALT are defined as ALT > 2 x baseline or > 300 U/L (patient is asymptomatic) ^a	ALT > 3 to ≤ 5 × ULN no symptoms
ALP (isolated)	

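### SAP Table 2-2 can count raised-baseline ALT values under × ULN labels they do not meet, and the matching protocol rows are nested with no stated precedence

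*Protocol*

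**What the plan says.** Protocol Appendix 2, Table 16-1, sets liver triggers and actions by ALT level. Three rows matter here. I call them the 5–8 row and the 3–5 rows, the latter split by whether the participant has symptoms.

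- **5–8 row.** The trigger is "> 5 to ≤ 8 × ULN If elevated at baseline: > 3 x baseline or > 300 U/L (whichever occurs first". The actions include "Repeat LFT within 48 hours" and "If elevation persists for more than 2 weeks, discontinue the study drug".
- **3–5 row with symptoms.** The raised-baseline alternative is "If elevated at baseline: > 2 x baseline or > 300 U/L (whichever occurs first". The actions include "Interrupt the study treatment (if possibly related to study treatment".
- **3–5 row without symptoms.** The alternative is the same. The action is "Repeat LFT within the next week", followed by close observation if the elevation is confirmed.

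The row above 8 × ULN has no raised-baseline alternative. The row that combines ALT with INR keeps its INR condition, so ALT alone does not meet it.

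SAP Section 2.7.3, Table 2-2, carries the same rules into the safety report. For the 5–8 row it states: "If ALT > ULN at baseline then criteria for ALT are defined as ALT > 3 x baseline or > 300 U/L". The two 3–5 rows are written the same way with 2 × baseline. The column of output labels still names the × ULN bands for everyone.

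Raised baselines are allowed. Exclusion criterion 12 (protocol Section 5.2) lists ALT, GGT and alkaline phosphatase in one sentence ending "alkaline phosphatase must not exceed 3 × ULN", so a screening ALT between 1 and 3 × ULN does not exclude a participant.

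**The concern.** A × ULN band has a floor and a ceiling. The raised-baseline alternatives have only a floor, and it is set on a different scale. Two problems follow.

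In the study report, a reader who sees a count beside a × ULN label will take it that those participants had ALT in that range. For raised-baseline participants the label need not be true, and one value can appear under two labels that exclude each other numerically.

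At the site, one laboratory result can satisfy two rows with different actions. Protocol Section 10.2.1 asks for a standardized process based on this table, so the investigator needs to know which row applies.

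**Working it through.** **Inputs.** BL is baseline ALT. The thresholds are those printed in Table 16-1 and Table 2-2. Neither document gives the ALT ULN in U/L, so I assume 40 and checked 33, 40, 45 and 55.

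**Rules as printed when BL > ULN.** An either/or threshold is met at the lower of its two values:

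- 3–5 rows: ALT > min(2 × BL, 300)
- 5–8 row: ALT > min(3 × BL, 300)
- top row: ALT > 8 × ULN

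**Step 1: nesting.** 3 × BL is larger than 2 × BL and 300 is common to both, so min(3 × BL, 300) ≥ min(2 × BL, 300). Every value that meets the 5–8 row therefore meets a 3–5 row; symptoms decide which one. This holds for any ULN. As a check, all whole-number ALT and baseline values were enumerated at the four ULNs, with baseline above ULN up to 3 × ULN and ALT up to 12 × ULN. Of 154,953 combinations, 101,304 met the 5–8 row and none of them escaped the 3–5 rows. These are grid points, not a forecast of participants.

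**Step 2: the nesting runs one way.** Values above 2 × BL, up to 3 × BL and not above 300 U/L meet only a 3–5 row. With ULN 40 this is 100–150 U/L at BL 50, 160–240 at BL 80, and 240–300 at BL 120. Above 300 U/L all these rows coincide.

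**Step 3: labels (ULN 40 assumed).**

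| BL | ALT | ALT/ULN | ALT/BL | Rows counted | Labels not met |
|---|---|---|---|---|---|
| 45 | 95 | 2.4 | 2.1 | 3–5 | 3–5 |
| 45 | 140 | 3.5 | 3.1 | 3–5 and 5–8 | 5–8 |
| 60 | 250 | 6.25 | 4.2 | 3–5 and 5–8 | 3–5 |
| 120 | 330 | 8.25 | 2.75 (but > 300 U/L) | 3–5, 5–8 and > 8 | 3–5 and 5–8 |

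Without reference to any U/L figure, write BL = b × ULN:

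- The 3–5 row can catch values at or below 3 × ULN when 2b < 3, i.e. b < 1.5.
- The 5–8 row can catch values at or below 5 × ULN when 3b < 5, i.e. b < 1.67.
- Because no ceiling is stated, either row can also catch values above its labelled band at any b.

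The two labels are disjoint, so any value counted in both rows fails at least one of them.

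**Step 4: would keeping the ceilings help?** Suppose the ≤ 5 and ≤ 8 × ULN limits were read as still applying. Overlap then remains only for b < 1.67, for example 150–200 U/L at BL 50 with ULN 40. The first example in the table would still carry a label it does not meet.

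**Step 5: actions for a value in both rows.**

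- With symptoms: one row interrupts treatment if possibly related. The other repeats the test and stops the drug only after more than two weeks of persistence.
- Without symptoms: the retest is due in 48 hours or within a week, and only one row has the two-week rule.

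I found no precedence or worst-category rule in either document.

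**The case against.** Four points on the other side deserve weight.

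*The actions are mostly compatible.* A repeat within 48 hours also satisfies a repeat within a week, and close observation fits with continued monitoring. For symptomatic participants, the monitoring instruction in the 5–8 row does not say to continue the drug, interruption is conditional on possible relatedness, and Section 10.2.1 leaves room for the investigator's judgement. This stands for asymptomatic participants. For symptomatic ones it narrows the problem without removing it, because the 3–5 row prompts immediate drug action and the 5–8 row does not.

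*Table 2-2 does not promise exclusive categories.* The SAP calls it criterion-based, prints the raised-baseline criteria in the definition column, and summarises chemistry data elsewhere by visit and by CTCAE grade. That is fair, and counting a participant in several criteria is not in itself an error. It does not make a × ULN label true for a value outside the stated range.

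*Earlier triggering is a threshold choice.* A reader might infer that the alternatives defeat their own purpose, because at mildly raised baselines they trigger at lower ALT than for a normal baseline. The arithmetic is right, but neither document states what the alternatives are for, so no contradiction can be shown.

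*The 300 U/L limit.* A reader might divide 300 by an assumed ULN of 33, get 9.1, and infer that the 5–8 row starts above 8 × ULN. The rule takes whichever threshold comes first. At that ULN the entry limit is 3 × 33 = 99 U/L and 3 × 99 = 297, so within the entry limit 300 U/L never sets the cut-off.

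**Conclusion.** SAP Table 2-2 is wrong as written for participants with baseline ALT above ULN: its criteria and its labels disagree. Protocol Table 16-1 has nested rows with different actions and no statement of which governs, and this needs reconciling, chiefly for symptomatic participants.

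The size is modest. One descriptive safety table and one appendix are affected, and no efficacy inference depends on either. With about 40 participants, one misplaced person moves a row by 1/40 = 2.5 percentage points.

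Two further inferences go too far. The rows do not overlap completely, since Step 2 shows a range that meets only the 3–5 rows. And raised baselines are permitted, but the documents give no frequency, so they cannot be called expected.

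The U/L examples rest on the assumed ULN of 40. The nesting and the conditions on b do not. The 3 × ULN limit applies at screening, while SAP Section 2.1.1.2 normally takes the Day 1 value as baseline; the nesting does not depend on that limit.

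**What to change.** **SAP Table 2-2.** Apply the × ULN rows strictly on × ULN for all participants. Put the baseline-multiple criteria in separate rows labelled as such, for example ALT above 2 × baseline or above 300 U/L among participants with baseline above ULN, and likewise for 3 × baseline. State whether a participant may be counted in more than one row. The cost is a few extra rows and a small programming change; the downside is a slightly longer descriptive table.

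**Protocol Table 16-1.** Reconcile the raised-baseline alternatives so that it is clear which row governs when a value meets more than one. The thresholds and actions are for the sponsor to decide. This costs more than the SAP change, because protocol Section 14.1 requires a written amendment with sponsor and ethics committee approval, and health authority approval where required. The SAP labels can be corrected without waiting for it.

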4.5 Risks and benefits

The risks associated with the use of iptacopan are those inferred by its pharmacology and the results of preclinical safety studies. The most relevant risks are described below and a complete description of preclinical safety findings is available in the Investigator Brochure. The safety results from the Phase 2 PHN studies (CLNP023X2204 and CLNP023X2201) are summarized

in the Investigator Brochure. Iptacopan at a dose of 200 mg b.i.d. has been generally safe and well tolerated in PNH patients enrolled in these studies.

Appropriate eligibility criteria, as well as study specific stopping rules for the study drug and recommended procedures are included in this protocol (see [Section 9.1.1](#)). The risk to participants in this trial will be minimized by compliance with the eligibility criteria and study procedures, including vaccinations prior to or up to 2 weeks after iptacopan initiation, close clinical monitoring with appropriate risk mitigation strategies, and periodic review of the safety data by an independent DMC. There is minimal risk to participants due to study procedures (mainly blood draws for laboratory assessments). One theoretical risk which is specific to PNH patients is the risk of hemolysis following discontinuation of treatment with a complement inhibitor. This is managed by specific discontinuation procedures outlined in [Section 9.1.1](#). Additionally, there is the possibility that vaccinations could increase complement activation and worsen hemolysis.

Iptacopan did not show any mutagenic, teratogenic or genotoxic potential in completed standard battery of genotoxicity testing. In addition, iptacopan was tested in embryo-fetal development studies in rats and rabbits and no iptacopan-related adverse fetal findings were detected in any of the studies. However, iptacopan has not been used in pregnant women, therefore, women of child-bearing potential must be informed that taking the study drug may involve unknown risks to the fetus if pregnancy were to occur during the study, and agree that in order to participate in the study they must adhere to the contraception requirements outlined in the exclusion criteria. If there is any question that the participant will not reliably comply, they should not be entered or continue in the study.

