9.1 Discontinuation and completion

9.1.1 Study treatment discontinuation and study discontinuation

Discontinuation of study treatment for a participant occurs when study treatment is stopped earlier than the protocol planned duration and can be initiated by either the participant or the investigator.

The investigator must discontinue study treatment for a given participant if, he/she believes that continuation would negatively impact the participant's well-being.

Study treatment must be discontinued under the following circumstances:

- Participant/guardian decision
- Any situation in which study participation might result in a safety risk to the participant

If a female becomes pregnant during the study, it is recommended to discontinue treatment with LNP023. However, after an individual benefit-risk assessment by the investigator, LNP023 continuation may be considered in exceptional circumstances. Counseling should be provided to the participant on the appropriate treatment for PNH during pregnancy. The outcome of the discussion with the participant, reflecting benefit-risk considerations, should be documented in the participant's file.

If treatment with iptacopan has to be discontinued immediately, i.e. because of a significant safety risk, appropriate replacement therapy must be offered to participants based on investigator's judgment and local availability (including starting anti-C5 antibody treatment if available).

Close monitoring of participants for signs and symptoms of hemolysis should be performed upon iptacopan discontinuation. It is recommended to monitor at minimum for: increase in LDH, decrease in hemoglobin level [REDACTED] increase in serum creatinine, thrombosis, and change in mental status. If serious hemolysis occurs, the Investigator should consider the following supportive treatments (and record them in the appropriate CRF pages):

- Blood transfusion (packed RBCs)
- Exchange transfusion if the PNH RBCs are >50% of the total RBCs by flow cytometry
- Corticosteroids
- Anticoagulation
- Any other supportive treatment or therapy as judged by the investigator

A visit one week after permanent discontinuation of iptacopan should occur for the following assessments: LDH, creatinine, hemoglobin, coagulation/thrombosis markers (Prothrombin time

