10.2 Additional Safety Monitoring

10.2.1 Liver safety monitoring

To ensure participant safety and enhance reliability in determining the hepatotoxic potential of an investigational drug, a standardized process for identification, monitoring and evaluation of liver events has to be followed.

Please refer to [Table 16-1](#) in [Appendix 2](#) for complete definitions of liver laboratory triggers.

Once a participant is exposed to study treatment, every liver event defined in [Table 16-1](#) should be followed up by the investigator or designated personnel at the trial site, as summarized below. Additional details on actions required in case of liver events are outlined in [Table 16-1](#). Repeat liver chemistry tests (i.e. ALT, AST, etc.) to confirm elevation.

These liver chemistry repeats will be performed using the central laboratory. If results will not be available from the central laboratory, then the repeats can also be performed at a local laboratory to monitor the safety of the participant. If a liver event is subsequently reported, any local liver chemistry tests previously conducted that are associated with this event should have results recorded on the appropriate CRF.

- If the initial elevation is confirmed, close observation of the participant will be initiated, including consideration of treatment interruption if deemed appropriate.
- Discontinuation of the investigational drug (refer to [Section 9.1.1](#)), if appropriate
- Hospitalization of the participant if appropriate
- Causality assessment of the liver event
- Thorough follow-up of the liver event should include:
 - Obtaining a more detailed history of symptoms and prior or concurrent diseases.
 - Obtaining a history of concomitant drug use (including nonprescription medications and herbal and dietary supplement preparations), exposure to environmental chemical agents, alcohol use, recreational drug use, and special diets.
 - Exclusion of underlying liver disease

These investigations can include based on investigator's discretion:

- Imaging such as abdominal US, Computed Tomography (CT) or Magnetic Resonance Imaging (MRI), as appropriate

- Considering gastroenterology or hepatology consultations.

All follow-up information and procedures performed must be recorded as appropriate in the CRF.

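### For symptomatic participants with normal baseline ALT, the liver table requires interruption at 3–5 × ULN but not at 5–8 × ULN, and drops the restart limit above 8 × ULN

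*Protocol*

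**What the plan says.** Three ALT rows of Protocol Appendix 2 (Section 16.2), Table 16-1, matter here.

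- **Symptomatic row**, "> 3 × ULN to ≤ 5 × ULN (accompanied by symptoms"): interrupt if the drug may be the cause. Restart is limited: "Study drug can be restarted only if alternative etiology is identified and liver enzymes return to baseline".
- **Row above 5 and up to 8 × ULN**, not divided by symptoms: re-test inside 48 hours, keep monitoring if the elevation persists, investigate the cause and record the event. The only drug action is "If elevation persists for more than 2 weeks, discontinue the study drug".
- **Row above 8 × ULN**: interrupt if the drug may be the cause. No restart condition is given.

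For participants whose ALT is already raised at baseline, the symptomatic row uses a different trigger with no upper limit. SAP Section 2.7.3, Table 2-2, repeats it: "criteria for ALT are defined as ALT > 2 x baseline or > 300 U/L (accompanied by symptoms"). Such participants can be enrolled, because exclusion criterion 12 (Protocol 5.2) sets only this limit: "Any single parameter of alanine aminotransferase (ALT), gamma-glutamyl transferase (GGT), alkaline phosphatase must not exceed 3 × ULN".

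Two general provisions also apply. Protocol 9.1.1 requires discontinuation in "Any situation in which study participation might result in a safety risk to the participant". Protocol 10.2.1 says that, after a confirmed elevation, "close observation of the participant will be initiated, including consideration of treatment interruption if deemed appropriate", and it sends the reader to Table 16-1 for the required actions.

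**The concern.** A table of liver stopping rules should not ask for less immediate protection as the injury marker rises and the symptoms stay the same. Here the symptomatic row stops at 5 × ULN, and the next row neither mentions symptoms nor requires interruption. A step that is mandatory at 4 × ULN becomes investigator judgement at 6 × ULN. The limit on re-exposure that applies after 4 × ULN with symptoms is not stated after 9 × ULN.

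The plan gives no reason why symptoms should stop mattering above 5 × ULN. Between 3 and 5 × ULN they decide the action: symptomatic participants are interrupted, while asymptomatic ones are re-tested and, if the elevation is confirmed, observed closely. That contrast points to a drafting gap more than a deliberate choice. Participant safety is at stake, not the efficacy inference.

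**Working it through.** The check is a walk through the table; no sample-size or power figure is involved. Conditions held fixed: a footnote b symptom is present, INR is at most 1.5, and there is no potential Hy's Law case and no jaundice, since each of these last three has its own stop or interruption rule.

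**Step 1. Baseline ALT at or below ULN**

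| ALT | Row met | Interruption required (if possibly related) | Restart limit |
|---|---|---|---|
| 4 × ULN | >3 to ≤5, symptomatic | Yes | Yes |
| 6 × ULN | >5 to ≤8 | No; discontinuation after more than 2 weeks | None |
| 9 × ULN | >8 | Yes | None |

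Interruption runs yes, no, yes as ALT rises. The restart limit runs yes, none, none.

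**Step 2. Baseline ALT of 1.5 × ULN** (an illustrative value that entry allows)

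The trigger for the symptomatic row is ALT above 2 × baseline or above 300 U/L.

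- ALT 4 × ULN: 4 / 1.5 = 2.67 × baseline. Trigger met.
- ALT 6 × ULN: 6 / 1.5 = 4.0 × baseline. Trigger met.
- ALT 8 × ULN: 8 / 1.5 = 5.33 × baseline. Trigger met.

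Interruption and the restart limit apply at all three values. At 6 and 8 × ULN the participant also meets the elevated-baseline trigger of the 5–8 × ULN row (above 3 × baseline). The table has no precedence rule, but re-testing and monitoring do not conflict with interrupting, so interruption remains required.

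**Step 3. Same ALT of 6 × ULN, same symptoms**

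- Baseline 1.5 × ULN, a 4-fold rise: interrupt if possibly related.
- Baseline at or below ULN, at least a 6-fold rise: no required interruption.

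The larger relative rise gets the weaker rule.

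**Step 4. Does the 300 U/L arm matter?** The documents give no ALT ULN in U/L. For assumed values of 35, 40 and 55 U/L, 300 U/L equals 300/35 = 8.57, 300/40 = 7.5 and 300/55 = 5.45 × ULN. The 2 × baseline arm is already met in every case in Step 2, so the results do not change.

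**Step 5. Where the restart limit appears.** Three ALT rows interrupt: above 8 × ULN, above 3 × ULN with INR above 1.5, and the symptomatic row. Two of the three carry the restart limit, as does the jaundice row. The highest ALT row does not.

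**The case against.** **The 5–8 × ULN row is in one respect stricter.** Its discontinuation after more than 2 weeks does not depend on relatedness, and the protocol glossary defines discontinuation as permanent. A case judged unrelated at 3–5 × ULN has no drug action in its row. This is correct, so the claim must be limited to the immediate action. For a symptomatic, possibly related case, the row still requires no drug action for the first 2 weeks.

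**Investigators must stop anyway.** Section 9.1.1 is mandatory and broadly worded, 10.2.1 requires interruption to be considered, and a further row of Table 16-1 asks for the same consideration for adverse events suggestive of liver toxicity. This stands as a limit: nothing instructs a site to keep dosing. But these provisions rest on judgement, whereas 10.2.1 describes a standardized process and relies on the table for required actions.

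**Such cases would be caught lower down.** Not necessarily. Scheduled visits are 28 days apart from Day 56 to Day 112 and throughout the extension, so the first raised value could already exceed 5 × ULN. On the way down from above 8 × ULN, a participant who is still symptomatic would re-enter the limited-restart row. The restart gap therefore matters mainly when symptoms resolve first.

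**Interruption is not free.** The protocol itself notes that "One theoretical risk which is specific to PNH patients is the risk of hemolysis following discontinuation of treatment with a complement inhibitor" (Section 4.5). The trial is aimed at countries where anti-C5 treatment is unavailable, so replacement may not exist. Fatigue and abdominal pain are also PNH symptoms. This is a real cost, but the table already accepts it at the lower ALT band, and the relatedness condition would still apply.

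**Conclusion.** The concern holds. For symptomatic participants with normal baseline ALT and none of the separate triggers, the immediate action required by Table 16-1 is weaker at >5 to ≤8 × ULN than at >3 to ≤5 × ULN. The restart limit is also absent from the highest ALT row. The baseline comparison assumes that when two rows are met, the actions of both apply.

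The size is modest. The documents give no expected frequency; in about 40 participants meeting several joint conditions, it should be low. No estimand, endpoint or efficacy analysis is affected, and the general duty to stop reduces the risk. It is worth correcting because it is a safety rule that runs the wrong way and is easily repaired.

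**What to change.** Preferred: add one bullet to the >5 to ≤8 × ULN row of Table 16-1, saying that if a footnote b symptom is present, treatment is interrupted when possibly related, and that restart follows the existing condition ("Study drug can be restarted only if alternative etiology is identified and liver enzymes return to baseline"). Add that same restart sentence to the >8 × ULN row. The counting categories in SAP Table 2-2 then stay as they are.

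Alternative: remove the upper limit from the symptomatic row so that it covers any symptomatic ALT above 3 × ULN, add the restart sentence to the >8 × ULN row, and align the label in SAP Table 2-2.

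Either route needs a protocol amendment with ethics committee approval and, where required, health authority approval (Protocol 14.1), but no new assessments. The clinical cost is possibly a few more interruptions, some set off by symptoms of PNH itself, each with the hemolysis risk noted above. The monitoring and supportive care in Section 9.1.1 for discontinuation are a ready model for managing them.
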